Title: **Effects of Short-term Curcumin and Multi-polyphenol Supplementation on the Anti-inflammatory Properties of HDL**

ClinicalTrials.gov ID: **NCT02998918**

Study Protocol and Statistical Analysis Plan

Date: 03/14/2018

Specific Aims

Atherosclerosis is a chronic inflammatory disease¹ underlying coronary artery disease, driven in part by the innate immune system, particularly macrophages.² The adhesion of leukocytes to the vascular endothelium, mediated by endothelial cellular adhesion molecules including vascular adhesion molecule-1 (VCAM-1) and intercellular adhesion molecule-1 (ICAM-1), is one of the crucial initial steps in atherogenesis. Elevated levels of high-density lipoprotein cholesterol (HDL-C) are associated with reduced risk for cardiovascular disease (CVD);³ however, interventions designed to increase HDL-C concentration in humans have yet to lead to reductions in cardiovascular events.⁴ A possible explanation for the failure of recent clinical trials is the structural and functional complexity of HDL particles, which have multiple cardioprotective properties, including anti-inflammatory, antioxidative, and reverse cholesterol transport activities. The anti-inflammatory effects of HDL include reduction of inflammatory cytokines and vascular leukocyte adhesion molecules.⁵ A recent study showed that dietary composition can affect HDL's anti-inflammatory properties, namely the ability to inhibit the expression of ICAM-1 and VCAM-1.⁶

Numerous studies have shown that polyphenols, including curcumin, quercetin, and resveratrol, exhibit multiple health benefits, including anti-inflammatory properties.⁷⁻¹³ Curcumin is a flavonoid polyphenol that is the active ingredient in the spice turmeric. Quercetin is one of the most abundant dietary flavonoids and is found in many fruits, vegetables, and beverages. Resveratrol is a non-flavonoid polyphenol present in a limited number of plant-derived foods, including grapes and peanuts. *In vitro* studies show these three polyphenols independently decrease VCAM-1 and ICAM-1 expression induced by tumor necrosis factor alpha (TNF α) in human endothelial cells,¹⁴⁻¹⁶ as well as increase cholesterol efflux to apolipoprotein A-I (apoA-I) and HDL in macrophages.¹⁷⁻²⁰ However, previous *in vitro* models used direct incubation with each polyphenol (i.e., HDL was directly exposed to the polyphenol in the cell culture, as opposed to incubation with plasma after consumption of the polyphenol), with doses much higher than found in typical human diets or supplements.

The health effects of polyphenols in humans are limited by their poor bioavailability, as they are rapidly metabolized and excreted. Recent studies have found that formulating poorly-absorbed molecules with phosphatidylcholine via phytosomes increases their bioavailability. For example, recent studies comparing curcumin phytosome (Meriva[®]) and standard curcumin formulations in humans found that the curcumin phytosome formulation increased curcuminoid bioavailability between 8- to 29-fold.^{21,22} To our knowledge, no study has examined the effects of polyphenol supplementation, particularly phytosome-formulated polyphenols, in humans on the ability of circulating plasma to inhibit the expression of cellular adhesion molecules or enhance cholesterol efflux capacity *in vitro*. Furthermore, it is unknown whether polyphenol supplementation modulates the ability of HDL particles to perform these same functions.

Therefore, the purpose of this study is to examine whether acute and short-term (1-week) polyphenol supplementation in humans affects inflammation measured at the whole plasma level, as well as the inflammatory and cholesterol efflux properties of HDL particles. We will test the effects of two supplements in a cross-over design: a curcumin phytosome and a multi-polyphenol supplement (containing curcumin phytosome, quercetin phytosome, and trans-resveratrol). We hypothesize that one of the mechanisms by which polyphenols exert a beneficial effect on inflammation and atherosclerosis is through its modulation of HDL particles. Specifically, we *hypothesize that polyphenol supplementation will improve the quality of HDL particles by increasing their anti-inflammatory and cholesterol efflux capacity properties, and that this benefit will be larger in the multi-polyphenol supplement compared to curcumin alone*. We will test this in the following aims: **Aim 1: Examine the acute (1 hr) and short-term (1 wk) effects of curcumin and poly-resveratrol supplementation in adults on VCAM-1 and ICAM-1 expression measured in (A) whole plasma and (B) the plasma HDL fraction. Hypothesis: Both acute and short-term polyphenol supplementation will significantly decrease VCAM-1 and ICAM-1 expression in whole plasma, which will be partly mediated by HDL-specific reductions in VCAM-1 and ICAM-1 expression. The acute effects of polyphenol supplementation at baseline will be attenuated but still significant after one-week of supplementation.**

Aim 2: Examine changes in cholesterol efflux capacity in J774 macrophages after one-hour and one-week of curcumin and poly-resveratrol supplementation in adults. Hypothesis: Both acute and short-term polyphenol supplementation will significantly increase HDL cholesterol efflux capacity.

Significance. Polyphenols are among the most studied dietary supplements, with a plethora of health benefits demonstrated in animal and *in vitro* models. However, human trials have been limited by the poor bioavailability of these compounds. Most human studies have only measured circulating inflammatory markers (e.g., TNF α , IL-6) and HDL-C levels, ignoring the possible effects of polyphenol supplementation on *in vitro* inflammatory properties such as VCAM-1 and ICAM-1 expression and HDL function. Given the shift in the HDL

field from quantity to quality, identifying dietary supplements that positively affect HDL functionality is important. The proposed study will overcome these limitations by employing phytosome formulations that increase bioavailability and measuring the effects of supplementation on the *in vitro* inflammatory properties of whole plasma and plasma HDL.

Research Strategy

Cross-over design. We plan to recruit 20 adults (aged 18-40 yrs) for this study. Subjects will be healthy, light drinkers (1-3 drinks/day or less), non-smokers, and not taking any medications or dietary supplements. Each volunteer will undergo a screening visit to ensure eligibility.

Following consent, each volunteer will complete 2 one-week trials in a randomized, blinded order separated by two weeks (**Figure 1**). Half the participants will be randomized to curcumin followed by polyresveratrol, the other half to polyresveratrol followed by curcumin.

Polyphenol supplementation. During each intervention period, the subjects will take two capsules of either curcumin phytosome (500 mg, Meriva-SR®, Thorne Research) or PolyResveratrol-SR® (100 mg curcumin phytosome, 100 mg quercetin phytosome, 100 mg green tea phytosome, 100 mg trans-resveratrol, 100 mg trans-pterostilbene; Thorne Research) twice daily for one week. Subjects will be advised to maintain their current diet and exercise patterns, while avoiding alcohol intake and restricting certain foods with high content of polyphenols, such as grapes, olive oil, curry, coffee, etc.

Laboratory measurements. Blood draws will be performed at baseline before and one hour after ingestion of one dose of the supplement, followed by the same sequence on the final day (Day 7) of the intervention. Thus, a total of 4 in-person visits including 8 blood draws will be performed over the 4-week trial period (**Figure 1**). All blood samples will be taken in the morning after an overnight fast and processed using the techniques described below. All measurements will be performed in [name] laboratory unless otherwise stated. The standard lipid profile will be measured using enzymatic methods. Whole plasma and plasma HDL concentrations of TNF- α and interleukin (IL)-6 will be determined by ELISA.

HDL isolation. The isolation of HDL particles from human plasma will be performed using gel filtration chromatography. Specifically, 370 μ L of plasma will be applied to two Superdex 200 10/300 GL increase columns arranged in series on an AKTA Pure 25 L FPLC system (GE Healthcare), as previously described.²³ The HDL fractions will be combined, aliquoted, and stored for the various assays (see below).

Cell adhesion molecule expression. Human umbilical vein endothelial cells (HUVECs) will be purchased and cultured as previously described.^{24,25} Confluent HUVECs will be incubated for 16 hrs with whole plasma or plasma HDL and then stimulated by TNF- α . After 4-5 hrs the cell-surface expression of VCAM-1 and ICAM-1 will be measured by flow cytometry.

Flow cytometry. Cell surface expression of VCAM-1 and ICAM-1 will be performed in the Flow Cytometry and Cell Sorting Core at the USC School of Medicine, as previously described.²⁵

Cholesterol efflux assay. Cholesterol efflux capacity will be assessed by measuring efflux of 3 H-labeled cholesterol from J774 macrophages to HDL plasma, as previously described.²⁶ Samples are run in triplicate on 96-well plates and results normalized to pooled control plasma included in each assay.

Statistical analysis. All analyses will be performed using SAS 9.3 (Cary, NC). The individual effects of each supplement will be tested using paired t-tests, while unpaired t-tests and mixed linear models will be used to compare the treatment effects between supplements. The effects of acute (1 hr) and short-term (1 wk) supplementation will be tested separately. Probability levels less than 0.05 will be considered significant.

Translation of Results into an R01 application. The successful completion of this pilot project will result in extensive preliminary data to be used for subsequent NIH R01, ADA junior faculty, and AHA scientist development grant applications focused on lifestyle factors (diet & exercise) and HDL function in the prevention and treatment of CVD and type 2 diabetes and their pathological precursors. The proposed research will provide data on the ability of resveratrol to decrease inflammation at the level of whole blood, as well as by modulation of the functional properties of HDL particles. Establishing the mechanisms by which resveratrol improves inflammation and HDL function is a necessary next step. As such, future studies are needed that examine the compositional changes to HDL in response to resveratrol supplementation, including changes in the HDL proteome, HDL lipidome, and HDL-associated microRNAs. These findings will need to be extended to other polyphenols and dietary supplements. This work will lead to new research initiatives on the biological mechanisms responsible for changes in the function and composition of HDL particles, particularly their anti-inflammatory properties, with dietary supplements.

[figure not shown]

Figure 1. Cross-over design of study.

References Cited

1. Ross R. Atherosclerosis — An Inflammatory Disease. *New England Journal of Medicine* 1999;340:115-26.

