All participants will be randomly assigned a subject number. Thus, all data will be recorded using the anonymous subject number. Only the PI ([name]) will have access to the identifiable information that links the subject id number to the individual. Blood samples will be stored in a freezer in the PI's laboratory, which is locked when not in use. The samples will be labeled using deidentified id numbers. Only personnel authorized by the PI will have access to the database and biological samples. All materials and data will be obtained specifically for research purposes.

c. Potential Risks

As this study involves the ingestion of dietary supplements and blood draws, there are potential for risks to the participants, which include:

- There is a risk when having blood drawn. Participants may experience discomfort, bruising and/or bleeding where the needle is inserted. Occasionally some people become dizzy, lightheaded, or feel faint. Infection may occur on rare occasions. Only trained staff will collect blood samples.
- There may be contraindications for the dietary supplements to be ingested as part of this study:
 - Meriva-SR is contraindicated in an individual with a history of hypersensitivity to any of its ingredients. Meriva-SR contains curcumin phytosome, a plant extract complexed with phosphatidylcholine, which is derived from soy. Phosphatidylcholine contains no soy protein. There are no other soy-based ingredients in Meriva-SR.
 - PolyResveratrol-SR is contraindicated in an individual with a history of hypersensitivity to any of its ingredients. PolyResveratrol-SR contains green tea phytosome and curcumin phytosome, plant extracts complexed with phosphatidylcholine, which is derived from soy. Phosphatidylcholine contains no soy protein. There are no other soy-based ingredients in PolyResveratrol-SR.
 - Although the doses used in the proposed study for both supplements is low (1g/day) and has a large safety threshold, it is possible for the participant to experience mild side effects, including headache, skin rash, minor flatulence and a yellowing of the stool. Although unlikely to happen, these side effects will stop after cessation of the supplement.

No alternative treatments or procedures are available to participants. Thus, if a participant is adverse to having blood drawn or experiences side effects from the supplementation, all procedures will be stopped and they will be removed from the study.

2. Adequacy of Protection Against Risks

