Storage and disposal of biological material: Biological samples will be stored at the University of South Carolina for up to ten years after the end of the study, at which time the samples will be destroyed. Samples will be stored in locked -80°C alarmed freezers located in a locked room. The laboratory coordinator and the PI have access to the keys to the freezers. The alarm system is triggered by opening the freezer, power outage or critical temperature rise, and is connected to the laboratory coordinator by means of an automatic telephone dialer. We have devised emergency procedures to salvage the samples in case of power outage. All samples will have study IDs with no personal identifiers of the participants. Participants can request to have their samples destroyed at any time by contacting the PI in writing.

3. Potential benefits of the proposed research to human subjects and others

Participants may experience clinical benefits from knowing some of their physiological parameters, such as blood lipid profile and blood pressure. Participants are expected to experience health benefits from ingesting the dietary supplements, particularly reduced inflammation. Individuals who do not qualify will be told the reasons for disqualification and referred for appropriate care. Therefore, the risk/benefit ratio is acceptable since potential risks of these research procedures are minimal and/or infrequent, and possible complications will be carefully monitored. Potential risks are reasonable in relation to anticipated benefits to health from the interventions.

4. Importance of the Knowledge to be Gained

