Systemic inflammation and HDL dysfunction is common in overweight, sedentary adults. These conditions lead to more serious health risks and diseases such as diabetes and cardiovascular disease. Polyphenols are among the most studied dietary supplements, with a plethora of health benefits demonstrated in animal and *in vitro* models. However, human trials have been limited by the poor bioavailability of these compounds. Most human studies have only measured circulating inflammatory markers (e.g., TNF α , IL-6) and HDL-C levels, ignoring the possible effects of polyphenol supplementation on *in vitro* inflammatory properties and HDL function. Given the shift in the HDL field from quantity to quality, identifying dietary supplements that positively affect HDL functionality is important. The proposed study will overcome these limitations by employing phytosome formulations that increase bioavailability and measuring the effects of supplementation on the *in vitro* inflammatory properties of whole plasma and plasma HDL.

5. Data and Safety Monitoring Plan

A Data and Safety Monitoring Plan (DSMP) will be implemented as described below to ensure the safety of all participants involved in the study and to ensure the validity and integrity of the data. If required by NIH, a Data Safety Monitoring Board (DSMB) will be established, with responsibility to monitor all aspects of the study, including those that require access to any blinded data. The operational plan and all members will be approved by the NIH Program Scientist.

The PI and the Project Coordinator will meet regularly on a continuous basis to review study progress and to examine reports of adverse incidents as well as participant recruitment and follow-up. All serious adverse events will be reported to the IRB within the required time frame, and if the event occurred as a direct result of participation in this study, an amendment may be made to the study protocol and consent form and the PI will request new IRB approval.

Adverse events include any event that occurs during the course of the study that results in a participant suffering physical or mental injury, pain or suffering. Adverse events can be major, such as a subject who suffers significant gastrointestinal pain/fluctuation from the supplementation, or minor such as a subject experiencing minor flatulence from supplementation. Deviations from the study's protocol are also considered an unexpected or notable event.

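### The blind covers only the order of the supplements, and nothing masks assay staff to draw time, which is the contrast the paired t-tests rest on

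*Combined protocol and SAP*

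**What the plan says.** **Blinding.** The cross-over design paragraph of the Research Strategy states that "each volunteer will complete 2 one-week trials in a randomized, blinded order separated by two weeks". There are two sequences: "Half the participants will be randomized to curcumin followed by polyresveratrol, the other half to polyresveratrol followed by curcumin". The only other mention is in the Data and Safety Monitoring Plan, where a board set up only if NIH requires it would monitor all aspects of the study, "including those that require access to any blinded data". Neither place says who is blinded, who holds the sequence list, or how the blind is kept.

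**Labels.** Under Sources of Materials, "All participants will be randomly assigned a subject number" and "The samples will be labeled using deidentified id numbers". The paragraph on storage of biological material adds "All samples will have study IDs with no personal identifiers of the participants". The Confidentiality paragraph describes the identification numbers as unique to each individual.

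**Assays.** One laboratory, whose name is removed from the public text, runs the measurements unless otherwise stated. VCAM-1 and ICAM-1 flow cytometry is done in a separate university core facility. Efflux samples are run in triplicate and normalized to pooled control plasma. None of the assay paragraphs mentions masking or run order.

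**Analysis.** Each supplement's own effect is tested by paired t-test, with the 1-hour and 1-week effects tested separately. Unpaired t-tests and mixed models compare the supplements. Section 1a of Protection of Human Subjects states that there is no placebo group.

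**The concern.** The outcomes of both aims are laboratory readouts: adhesion molecule expression in whole plasma and in the HDL fraction, and cholesterol efflux. If bias from knowing the sample's status enters this trial, the laboratory is the likely place. Combining HDL fractions, setting flow cytometry gates and deciding on repeat runs can each involve judgement. How much is an assumption here, because the plan gives no rules for these steps.

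The hypotheses are directional: adhesion molecule expression should fall after supplementation and efflux should rise. Someone who knows that a tube is post-dose knows which way the result is expected to go. Without a placebo period, a reading shift between time points has no counterpart to be subtracted from, so it enters the within-supplement estimate in full. The plan intends these results as preliminary data for larger grant applications, so a spurious effect would be carried forward.

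**Working it through.** **1. The samples.** 2 supplement periods × 2 visits (baseline, Day 7) × 2 draws (pre-dose, 1 hour) = 8 draws at 2 × 2 = 4 visits. This reproduces the plan's 8 draws and 4 visits. For 20 participants, 20 × 8 = 160 draws.

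**2. What each stated safeguard hides.**

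| Safeguard in the plan | Hides identity | Hides supplement | Hides draw time and visit |
|---|---|---|---|
| Blinded order | no | yes, for whoever is covered (not stated) | no |
| De-identified study ID | yes | no | no |
| Triplicates and pooled control plasma (efflux) | no | no | no |

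No safeguard addresses the last column. On the natural reading, the study ID is one number per person and is therefore shared by all 8 of that person's samples. Some further mark must tell the 8 apart. The plan does not say what that mark is or keep it from assay staff.

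**3. Where a shift would go.** Let b be a systematic reading shift of later tubes relative to earlier ones.

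- Within one supplement, the mean paired difference = true effect + b. The paired t-test cannot separate the two.
- Between supplements, the comparison = (true effect of one + b) − (true effect of the other + b) = difference in true effects. A common b cancels. Only a shift that differs by supplement would remain.

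**4. Illustrative size.** The documents give no SD, effect size or bias figure, so b is assumed, in SDs of the paired difference. The inputs are n = 20 from the plan, significance level 0.05 from the plan, and a two-sided test (assumed, since sidedness is not stated). With no true effect, the noncentrality is δ = b × √20, and

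P(significant) = 1 − F(t; 19, δ) + F(−t; 19, δ),

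where F is the noncentral t distribution function with 19 degrees of freedom and t is its central 97.5% point.

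| Assumed shift b | δ = b × 4.472 | False-positive rate |
|---|---|---|
| 0 | 0 | 5.0% |
| 0.1 | 0.447 | 7.1% |
| 0.2 | 0.894 | 13.6% |
| 0.3 | 1.342 | 24.7% |
| 0.5 | 2.236 | 56.5% |

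**The case against.** The strongest reply has four parts.

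- **The blind is worth more than it looks.** In a two-sequence crossover, hiding the order hides the supplement in each period. If the blind covers the laboratory, knowing the participant and the period still does not reveal the supplement. This stands.
- **Nothing shows that labels unmask.** No text says that a label shows visit or time, and codes specific to each tube are not excluded. This stands as far as it goes: the gap is a missing masking rule, not a demonstrated leak. It does not remove the gap, because both labelling sentences are about confidentiality and storage, and neither rules out that assay staff can read the time point.
- **Practice may limit discretion.** Flow cytometry is done in a separate core, and efflux is run in triplicate against pooled control plasma. These reduce assay noise and perhaps the scope for judgement. They are not masking, and none is stated for the core.
- **The bias is hypothetical, and the study is a 20-person pilot.** The assumed shifts have no source in the documents, and a common shift would not disturb the comparison that tests whether the multi-polyphenol product does better. Both are true. The within-supplement tests, on which the hypotheses of both aims rest, remain exposed.

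**Conclusion.** The concern holds for draw time and visit. The plan states no masking of laboratory or core staff to pre-dose versus 1 hour or to baseline versus Day 7, and the blind that it does state cannot supply it. The within-supplement paired t-tests are affected. The between-supplement comparison is largely protected, provided that any shift is common to both supplements. The size of any bias is unknown. The figures of about 14% at 0.2 SD and about 25% at 0.3 SD depend on assumed shifts, n = 20 and a two-sided 0.05 test.

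Two stronger readings are tempting and not supported.

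- A reader might infer that the laboratory can know which supplement a tube follows. That would need the sequence list, and the documents do not say whether the laboratory is covered by the blind. The point is unspecified, not shown.
- A reader might infer that participants or staff could identify the period from side effects or curcumin content. The listed "mild side effects, including headache, skin rash, minor flatulence and a yellowing of the stool" are given for both supplements together, and both contain curcumin phytosome. The stated curcumin phytosome amounts differ (500 mg against 100 mg), but the five listed components of the other product also total 5 × 100 = 500 mg, and capsule appearance is not described.

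This is an inexpensive improvement that should be made. It is not a flaw that invalidates the design.

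**What to change.** 1. **Sources of Materials and the storage paragraph, changed together so that they agree.** For assay aliquots, replace study-ID labelling with a random code per tube that shows neither participant, visit, draw time nor supplement.
2. **Key and batching.** An existing team member who runs no assays holds the key and assigns each participant's 8 samples to the same assay batch in random order. Without the batching rule, hiding the participant could scatter one person's paired samples across runs. The plan already freezes aliquots for later use, so holding them for a common batch fits.
3. **Lock before decoding.** HDL pooling, flow cytometry, efflux and ELISA data are finalised and locked before the key is opened. The rule applies to the core facility as well.
4. **Cross-over design paragraph.** State for each group whether it is blinded (participants, clinic staff, laboratory staff, core staff), and who holds the sequence list.

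The cost is a label list that must be kept and batches that must be planned. There are no extra visits, blood draws or assays. If masking of this kind is already practised, the change is a few sentences.

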During each intervention period, the subjects will take two capsules of either curcumin phytosome (500 mg, Meriva-SR®, Thorne Research) or PolyResveratrol-SR® (100 mg curcumin phytosome, 100 mg quercetin phytosome, 100 mg green tea phytosome, 100 mg trans-resveratrol, 100 mg trans-pterostilbene; Thorne Research) twice daily for one week. After taking the supplement for one week, there will be a two week washout period, followed by one week of taken the second supplement. Aside from the first and last doses, which will be administered in the clinic, all other doses will be self-administered. Subjects will be advised to maintain their current diet and exercise patterns, while avoiding alcohol intake and restricting certain foods with high content of polyphenols, such as grapes, olive oil, curry, coffee, etc.

All participants will receive clear instructions for participation in the study. We plan to give each volunteer a total of \$125 for completing the study, which breaks down to \$25 per visit to the clinic (screening, baseline visit for supplement 1, post-supplement 1 visit, baseline for supplement 2, post-supplement 2 visit).

b. Sources of Materials

Blood draws will be performed at baseline before and one hour after ingestion of one dose of the supplement, followed by the same sequence on the final day (Day 7) of the intervention. This sequence will be repeated during the trial with the second supplement. Thus, a total of 4 in-person visits including 8 blood draws

will be performed over the 4-week trial period. All blood samples will be taken in the morning after an overnight fast from the antecubital vein. The blood will be immediately spun down and aliquoted into plasma and serum fractions and frozen for future use. At the baseline visit, anthropometric data will be measured including height, weight, waist circumference, blood pressure. Data on physical activity and family history will be ascertained via questionnaire and results will be recorded on a paper form or in a computer database. Paper forms will be stored in locked file cabinets and electronic files will be password-protected in an office that is locked when not in use.

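### The between-supplement comparison names unpaired t-tests for a crossover, which discards the pairing and cannot adjust for period, beside mixed models whose terms are not given.

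*Combined protocol and SAP*

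**What the plan says.** Under Research Strategy, Cross-over design, each of 20 adults takes both supplements for one week, two weeks apart: "Half the participants will be randomized to curcumin followed by polyresveratrol", and the other half take them in the reverse order. Each period has its own baseline. Under Laboratory measurements, "Blood draws will be performed at baseline before and one hour after ingestion of one dose of the supplement", with the same pair of draws on Day 7. Protection of Human Subjects, 1b, adds that "This sequence will be repeated during the trial with the second supplement".

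The whole analysis plan is the Statistical analysis paragraph. Each supplement's own effect is tested by paired t-test. Between supplements, "unpaired t-tests and mixed linear models will be used to compare the treatment effects between supplements". It adds that "The effects of acute (1 hr) and short-term (1 wk) supplementation will be tested separately", at a 0.05 level. No period, sequence or participant term is named anywhere in the document, and no rule ranks the two between-supplement methods.

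On losses, Protection of Human Subjects, 1c, says of participants with side effects that "all procedures will be stopped and they will be removed from the study". No rule for missing data or replacement is given.

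**The concern.** The between-supplement comparison carries a stated hypothesis in Specific Aims, that "this benefit will be larger in the multi-polyphenol supplement compared to curcumin alone". Every participant contributes to both sides of that comparison. A crossover is efficient because differences between people cancel within each person, and an unpaired t-test gives that up. With 20 people, a real difference could easily be missed.

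The unpaired test also has no place for a period term. With 10 people in each order, a period effect cancels from the difference in supplement means. If completers are uneven, it does not cancel fully, and part of it would be read as a difference between supplements.

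**Working it through.** The plan states no power, SD or effect size, so it has no figure to reproduce.

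**Inputs.** From the document: 20 participants, 10 per sequence, level 0.05 (taken as two-sided). Assumed: within-period change with SD 1 on each supplement; correlation ρ between a person's two changes, 0.5 for the main figures; a true difference of 0.65 SD for power; a period effect of 0.5 SD for the leakage figures; and all loss counts.

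**1. Standard error, 10:10, no losses.**
- Reported by the unpaired test: √(2/20) = 0.316.
- True value: √(2(1−ρ)/20) = √(1/20) = 0.224 at ρ = 0.5.

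**2. What this does to the test (no period effect).**
- Unpaired, 38 df: a difference must exceed about 2.024 × 0.316 = 0.640 SD. Power at 0.65 SD: (0.65 − 0.640)/0.224 = 0.04, so a little over one half.
- Paired and period-adjusted, 18 df: 2.101 × 0.224 = 0.470 SD. Power: (0.65 − 0.470)/0.224 = 0.80, so about 0.79.
- Simulation agrees: 0.52 to 0.53 against 0.78 to 0.79. With no true difference, the unpaired test rejects 0.7% to 0.8% of the time and the adjusted analysis about 5%.

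**3. Dependence on the correlation.** Simulated, 10:10, no period effect:

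| ρ | Unpaired rejection, no difference | Power, unpaired | Power, adjusted |
|---|---|---|---|
| 0 | 4.9% | 0.52 | 0.49 |
| 0.3 | 2.1% | 0.52 | 0.64 |
| 0.5 | 0.7–0.8% | 0.52–0.53 | 0.78–0.79 |
| 0.6 | 0.4% | 0.53 | 0.87 |

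**4. Share of a period effect entering the simple comparison.**
- Both periods lost: (n1 − n2)/(n1 + n2). 10:8 gives 2/18 = 0.11; 10:6 gives 4/16 = 0.25.
- Period-1 data kept, losses in one sequence: with m people left in period 2 of that sequence, |m/(10+m) − 10/20|. m = 8 gives |0.444 − 0.5| = 0.056; m = 6 gives |0.375 − 0.5| = 0.125.
- Each sequence loses 2 people on the same supplement: one supplement has 8 of 18 values from period 2, the other 8 of 16, so the share is 0.056.

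**5. Size of that leak.** With a 0.5 SD period effect on the change:
- 10:8 gives 0.111 × 0.5 = 0.056 SD.
- 10:6 gives 0.25 × 0.5 = 0.125 SD, half the true standard error of 0.250 for the simple difference. The unpaired test would report √(2/16) = 0.354.
- The same-supplement pattern gives 0.056 × 0.5 = 0.028 SD, about a ninth of 0.250.
- Rejection at 10:6 with no supplement difference: 1.3% unpaired, 4.8% paired without period, 5.0% with period.

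**6. Losses unrelated to sequence or supplement.** Either sequence is equally likely to lose more people, so the signed share averages 0. The mean absolute share is 0.053 for 2 lost and 0.084 for 4 lost, or 0.026 and 0.042 SD at a 0.5 SD period effect. These last figures are mean absolute conditional biases.

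**7. After the fix.** With supplement and period in the model the share is 0 in every pattern checked. Standard error against the simple paired difference, ρ = 0.5: 0.258 against 0.250 at 10:6; 0.237 against 0.236 at 10:8; 0.248 against 0.250 when 4 are lost from period 2 of one sequence only.

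**The case against.** **A suitable method is already named.** A mixed model can hold participant and period terms, and terms left unstated have not been ruled out. This stands in part: the document does not show that the mixed model would omit period. For that model, the supportable point is only that its terms, and its standing relative to the t-test, should be stated. The unpaired test is named in its own right and is wrong for the design.

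**The unpaired test might be the valid one between sequences.** Applied to within-person period differences, such a test would remove period. But the sentence compares supplements, so the text does not support that reading.

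**The period leak needs two things the document does not establish:** uneven losses, and a period effect on the change itself. This largely stands. A constant shift in level cancels because each period has its own baseline. Of side effects, section 1c says: "Although unlikely to happen, these side effects will stop after cessation of the supplement". Section 2b would let some participants resume after seeing a physician. Efflux results are normalised to pooled control plasma in each assay. For the acute pair at a period's first visit, a later removal in that period comes too late to lose it.

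**The study is a pilot.** True, but that does not make an analysis that ignores the pairing suitable. A small sample makes the lost precision matter more.

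A reader might infer that the planned comparison is biased on average, or that it produces false positives. Neither is supported. The average bias is zero under losses unrelated to sequence or supplement, and the unpaired test rejects too rarely when the correlation is positive.

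**Conclusion.** Wrong as written. The main harm is lost precision, which occurs with complete data and no period effect: at correlation 0.5, about 0.7% rejection instead of 5%, and power of about 0.53 against 0.79 for a 0.65 SD difference. This rests on the assumed correlation between a person's two changes, for which the document gives no figure. At 0.3 the gain in power is smaller, and at zero there is none.

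The period leak is secondary. It is conditional on a given pattern of uneven losses, small against the standard error, and no excess of false positives is claimed. Loss counts and the size of the period effect are assumptions. The case for change does not depend on the leak, but the same change removes it.

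**What to change.** In Statistical analysis, drop the unpaired t-tests. Take the between-supplement difference from one mixed linear model per outcome, run separately for acute and one-week effects. Model the within-period change, with fixed supplement and period terms and a participant random effect. A sequence term is optional: the leak is already zero without it. Use all available data from every randomised participant, including those with one period only, and say that this model decides the comparison.

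Define the changes:
- One-week: Day 7 pre-dose minus baseline pre-dose in the same period.
- Acute: one hour minus pre-dose at the same visit, with the baseline and Day 7 pairs analysed separately.

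The paired t-tests may stay as within-supplement summaries. Report removals by supplement and period.

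The cost is analysis wording, with no added visits or samples. The standard error is at most about 3% larger than that of the simple paired difference in the loss patterns checked. The model does not correct for losses that depend on the unobserved response.
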